6.4.6 Electrocardiogram

12-Lead ECGs data (PR, QRS, QT, QTcF, and HR) will be documented for subjects during study at baseline (Visit 1 and Visit 3), Day 50 (Visit 8), at End of Study (Visit 12) and at Cardiac Follow-up (Visit 14).

Analysis of Echocardiograms will be included in a separate report from Biomedical Systems.

6.4.7 Doppler Echocardiography

Doppler echocardiography will be conducted at a facility with experience for the subject's age at Screening, Maintenance period (Visit 8), End of study (Visit 12), and Cardiac Follow-up (Visit 14). ECHO uses ultrasound technology to examine the heart or blood vessels. An ECHO uses high frequency sound waves to create an image of the heart while the use of Doppler technology allows determination of the speed and direction of blood flow by utilizing the Doppler effect. Predetermined standard guidelines on the proper evaluation of certain measurements, as well as abnormality thresholds, were constructed by the sponsor's IPCAB prior to study initiation. These thresholds are provided in the table below:

Signs on ECHO indicative of potential Valvulopathy 
• valve regurgitation (aortic or mitral)• \geq mild valve regurgitation (tricuspid,	Normal Values for Children 2-18 years 
• No regurgitation• Mean Mitral valve gradient < 4 mmHg
---	--

or pulmonary) 
 • Mean Mitral valve gradient ≥ 4 mmHg • Mean Aortic valve gradient ≥ 15 mmHg • Mean Tricuspid valve gradient > 4 mmHg • Mean Pulmonary valve gradient > 21 mmHg 	
 • Mean Aortic valve gradient < 15 mmHg • Mean Tricuspid valve gradient < 4 mmHg • Mean Pulmonary valve gradient < 21 mmHg
Signs on ECHO indicative of pulmonary hypertension a. Tricuspid Regurgitation Jet velocity > 2.8 msec with or without the following findings OR b. One of the following findings in the absence of being able to measure Tricuspid Regurgitation Jet velocity: 
 i. Change in right ventricle/left ventricle basal diameter ratio > 1.0 ii. Right ventricular acceleration time < 100 msec iii. Dilatation of the inferior caval vein (diameter > 21 mm and $< 50\%$ inspiratory decrease) and/or right atrium iv. Change in the geometry of the interventricular septum in systole (flattening) with left ventricular eccentricity index > 1.1 in systole and/or in diastole v. Early diastolic pulmonary regurgitation velocity > 2.2 m/sec vi. Tricuspid Anular Plane Systolic Excursion below 18 mm or below Z-score – 2 	

Results of ECHOs will be presented in a separate report from Biomedical Systems.

6.4.8 Tanner Staging

Tanner Staging will be assessed for subjects > 7 years old during the study at baseline period (Visit 3) and End of study (Visit 12). Conceptually, pubertal maturation can be described in terms of sequence, timing, and tempo. Puberty consists of a series of predictable events, and the sequence of changes in secondary sexual characteristics has been categorized by several groups. The onset and progress of pubertal changes will be recorded on a 5 point scale for boys and girls separately. Boys are rated for genital development and pubic hair growth through stage I to stage V. Girls are rated for breast development and pubic hair growth through stage I to stage V.

The number and percentage of subjects in each Tanner Stage will be presented for all visits by treatment group separately for boys and girls overall and also broken out for the following age groups:

> 7 years to ≤ 11 ,

> 11 years to ≤ 15 ,

> 15 years to ≤ 18 .

All Tanner staging data will be presented in the subject data listing.

6.4.9 Laboratory Parameters

Laboratory safety parameters will be analyzed by a central laboratory using standard validated methods.

All laboratory safety data will be collected as per the schedule of assessments given in Table 2.

The following laboratory parameters will be summarized:

- Hematology: hemoglobin, hematocrit, erythrocytes, erythrocyte mean corpuscular volume, leukocytes, mean corpuscular hemoglobin, mean corpuscular hemoglobin concentration, neutrophils, lymphocytes, monocytes, eosinophils, basophils and platelets
- Blood Biochemistry: albumin (ALB), alkaline phosphatase (AP), alanine aminotransferase (ALT; SGPT), aspartate aminotransferase (AST; SGOT), bicarbonate, blood urea nitrogen (BUN), calcium (Ca), carbon dioxide (CO₂), chloride (Cl), creatinine, creatine kinase, gamma-glutamyl transferase (GGT), globulin, glucose, lactate dehydrogenase (LDH), phosphorus, potassium (K), sodium (Na), thyroid function (T₃, T₄, and thyroid stimulating hormone [TSH]), total bilirubin, direct bilirubin, total cholesterol, total protein, triglycerides, uric acid.
- Tests of growth and precocious puberty: Growth hormone (GH), insulin-like growth factor-1 (IGF-1, low sensitivity), prolactin, Luteinizing Hormone (LH), Follicle Stimulating Hormone (FSH), testosterone, estradiol
- Coagulation: Prothrombin time (PT)/International normalized ratio (INR), activated partial thromboplastin time (PTT)
- Whole blood cannabidiol (CBD)
- Urinalysis: analysis for pH, glucose, ketones, nitrite, protein, bilirubin, urobilinogen, leukocyte esterase, and occult blood. Microscopic analysis will be performed for blood, all cell types, and casts.
- Urine pregnancy test: Urine pregnancy testing will be performed in female subjects of childbearing potential.
- Urine THC panel

Observed continuous laboratory data will be summarized by type of laboratory test/parameter by treatment group. Changes from baseline will also be presented for all continuous laboratory parameters by treatment group over time.

Categorical laboratory parameters will be summarized by presenting the number and % of subjects in each category by visit and by treatment arm.

All laboratory values (including invalid values, reference ranges, and possible flags (low, high.)) will be presented in the subject data listings.

A listing of subjects with Potentially Clinical Significant laboratory results will be provided. In this listing, those values outside the sponsor defined alert ranges will be marked and further available details about clinical relevance and diagnosis will be added.

A special listing will be presented which will provide for each subject and each lab parameter the maximum out-of-range value over both Baseline and during the T+M period. The visit on which this highest or lowest value occurred will be included.

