4.1 INCLUSION CRITERIA

Subjects must meet all of the following inclusion criteria to be enrolled into the study:

1. Subject is male or non-pregnant, non-lactating female, age 2 to 18 years, inclusive as of the day of the Screening Visit. Female subjects of childbearing potential must not be pregnant or breast-feeding. Female subjects of childbearing potential must have a negative urine pregnancy test. Subjects of childbearing or child-fathering potential must be willing to use medically acceptable forms of birth control (see [Section 4.4](#)), which includes abstinence, while being treated on this study and for 90 days after the dose of study drug.
2. Subject must have documented medical history to support a clinical diagnosis of Dravet syndrome, where convulsive seizures are not completely controlled by current antiepileptic drugs.
3. Subjects must meet all of the following 5 criteria:
 - a. Onset of seizures in the first year of life in an otherwise healthy infant.
 - b. A history of seizures that are either generalized tonic-clonic or unilateral clonic or bilateral clonic, and are prolonged.
 - c. Initial development is normal.
 - d. History of normal brain magnetic resonance imaging (MRI) without cortical brain malformation.
 - e. Lack of alternative diagnosis.

4. Subjects must meet at least one of the following 3 criteria:
 - a. Emergence of another seizure type, including myoclonic, generalized tonic-clonic, tonic, atonic, absence and/or focal has developed after the first seizure type.
 - b. Prolonged exposure to warm temperatures induces seizures and/or seizures are associated with fevers due to illness or vaccines, hot baths, high levels of activity and sudden temperature changes and/or seizures are induced by strong natural and/or fluorescent lighting, as well as certain visual patterns.
 - c. Genetic test results consistent with a diagnosis of Dravet syndrome (pathogenic, likely pathogenic, variant of unknown significance, or inconclusive but unlikely to support an alternative diagnosis.)
5. Subject must have had \geq 4 convulsive seizures (tonic-clonic, tonic, clonic) per 4-week period for 12 weeks prior to screening, by parent/guardian report to investigator or investigator medical notes (**Cohort 2 only**).
6. All medications or interventions for epilepsy (including ketogenic diet [KD] and vagal nerve stimulation [VNS]) must be stable for at least 4 weeks prior to screening and are expected to remain stable throughout the study.

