3.2 COHORT 2 STUDY TREATMENT

The study period of cohort 2 subjects comprises a Baseline period (6 weeks), a T+M period (15 weeks: (21 days for dose titration + 12 weeks maintenance), a Taper period or transition period, and a Post Dosing visit after study completion or early termination.

Upon completion of the Baseline Period, subjects who qualify for the study will be randomized (1:1) in a double-blind manner to receive ZX008 (0.5 mg/kg/day, 20 mg/day maximum) or placebo. Randomization will be stratified by age group (<6 years, \geq 6 years) to ensure balance across treatment arms, and initially it was hoped that at least 40% of subjects will be in each age group. The actual % of subjects in each stratum may be different from this goal. Subjects will be assigned a randomization number by the IVR/IWR system upon confirmation that the subject qualifies for enrollment in the Titration Period. All subjects will be titrated to their randomized dose during the Titration Period. Titration will occur in 3 steps starting with a 0.2 mg/kg/day dose of ZX008 (or placebo equivalent) on Study Days 1-7, increased to a dose of 0.4 mg/kg/day on Study Day 8-14, and then increased to a dose of 0.5 mg/kg/day on Study Days 15-21; the maximum daily dose at any point is 20 mg/day. The duration of the titration period will be 21 days.

There will be cardiac safety follow-up of 3 to 24 months after study drug discontinuation for early termination or for subjects who complete the study but do not enroll in the open-label extension study. These results will be presented elsewhere.

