Table	14.3.1.4b	Serious TEAEs by Primary SOC and PT – Safety Population
Table	14.3.1.5b	Study Drug Related TEAEs by Primary SOC and PT – Safety Population
Table	14.3.1.6b	TEAEs by Maximum Severity by Primary SOC and PT – Safety Population
Table	14.3.1.7b	Treatment-Emergent Adverse Events Occurring in $\geq 5\%$ of Subjects by MedDRA System Organ Class and Preferred Term - Safety Population
Table	14.3.1.8b	Overview of Number of Subjects with Treatment-Emergent Adverse Events of Special Interest (AESI) – Safety Population
Table	14.3.1.9b	Adverse Events of Special Interest (AESI) by MedDRA System Organ Class and Preferred Term – Safety Population
	14.3.2	Listings of Deaths, Other Serious and Significant Adverse Events

Table	14.3.2.1b	Listing of Deaths – Safety Population
Table	14.3.2.2b	Listing of SAEs – Safety Population
Table	14.3.2.3b	Listing of Discontinuations Due to AE – Safety Population
	14.3.4	Laboratory value
Table	14.3.4.1b	Laboratory Parameters – Hematology – Safety Population
Table	14.3.4.2b	Laboratory Parameters – Biochemistry – Safety Population
Table	14.3.4.4.1b	Laboratory Parameters – Urinalysis (Quantitative Parameters) – Safety Population
Table	14.3.4.4.2b	Laboratory Parameters – Urinalysis Categorical – Safety Population
Table	14.3.4.5b	Tests of Growth, Precocious Puberty and Thyroid Function – Safety Population
Table	14.3.4.6b	Epilepsy Genotype Panel – Safety Population
	14.4.1	Vital Signs
Table	14.4.1.1b	Vital Signs Parameters – Safety Population
	14.4.4	Tanner Staging
Table	14.4.4.1b	Tanner Staging by Age Group for Boys – Safety Population
Table	14.4.4.2b	Tanner Staging by Age Group for Girls – Safety Population
	14.4.5	Columbia-Suicide Severity Rating Scale (C-SSRS)
Table	14.4.5.1b	Columbia Suicide Severity-Rating Scale (C-SSRS) - Number of Subjects with Suicidal Ideation, Suicidal Behavior, and Self-Injurious Behavior without Suicidal Intent based on the C-SSRS – Safety Population
Table	14.4.5.2b	Columbia Suicide Severity-Rating Scale (C-SSRS) - Shift Table of Changes in C-SSRS Categories During Treatment - Safety Population
	14.4.6	Brief Rating Inventory of Executive Function- (BRIEF)
Table	14.4.6.1b	Brief Rating Inventory of Executive Function Preschool Version (BRIEF-P) – Safety Population
Table	14.4.6.2b	Brief Rating Inventory of Executive Function (BRIEF) – Safety Population
	16.2	Subject data listing
	16.2.1	Subject disposition and discontinuation
Listing	16.2.1.1b	Subject Completion/Discontinuation
	16.2.2	Protocol deviations

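### Puberty hormones are summarised by arm pooled over both sexes and ages 2 to 18, so no committed summary of them is suited to showing early pubertal change in a few children aged 7 or under

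*SAP*

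**What the plan says.** SAP 6.4.9 puts GH, IGF-1, "prolactin, Luteinizing Hormone (LH), Follicle Stimulating Hormone (FSH), testosterone, estradiol" under tests of growth and precocious puberty. The summary rule is the one for every continuous laboratory value: "Observed continuous laboratory data will be summarized by type of laboratory test/parameter by treatment group", and "Changes from baseline will also be presented for all continuous laboratory parameters by treatment group over time". Neither sentence mentions sex or age. Appendix 1 lists a single table for these tests, 14.3.4.5b, titled "Tests of Growth, Precocious Puberty and Thyroid Function". Protocol 4.1 admits both sexes, "age 2 to 18 years, inclusive as of the day of the Screening Visit".

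The adjacent section treats pubertal data differently. Under SAP 6.4.8, "Tanner Staging will be assessed for subjects > 7 years old during the study", and the stages are shown "by treatment group separately for boys and girls overall and also broken out for the following age groups", namely three bands that start above 7 years.

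Two clauses touch on age. SAP 6.1.3 permits, but does not require, selected safety outputs for under 6 and for 6 and over. Protocol 10.5.2 promises age-group repeats of selected safety summaries. Neither names the hormones or mentions sex. On the age mix, SAP 3.2 says "initially it was hoped that at least 40% of subjects will be in each age group" and adds that the actual split may differ.

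**The concern.** These hormones are drawn at six Cohort 2 visits (Protocol Table 12) to detect effects on growth and early puberty. Expected values depend on sex and pubertal stage, which is presumably why the Tanner tables are split. In a summary pooled over both sexes and ages 2 to 18, a rise that would be abnormal at age 4 can sit well inside the spread set by older children. Randomisation is stratified only at age 6, so the number of adolescents and the sex mix per arm are left to chance, and raw arm means can differ for that reason alone.

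At stake is the randomised comparison. Comparing laboratory parameters between arms is a stated safety objective (Protocol 2.3, SAP 2.4). For the youngest children, the planned hormone table is poorly placed to deliver that comparison on this question.

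**Working it through.** The plan states no figure on this point, so there is none to reproduce. The check has four steps.

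**1. What is committed for a child aged 7 or under**

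- Tanner stage: none (SAP 6.4.8).
- Hormone summary: by arm only (SAP 6.4.9). The under-6 split is optional and would still mix boys with girls and put 6-year-olds with adolescents.
- By-arm count of high values: none. Counts are specified only for categorical parameters.
- Extreme-value listing: SAP 6.4.9 promises one covering every laboratory parameter. Appendix 1 names them only for hematology (16.2.8.1.2b), biochemistry (16.2.8.2.2b) and urinalysis (16.2.8.4.2b). Hormones get a plain listing, 16.2.8.5b.

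**2. How many children that could be**

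Assume a share s under 6, and ages uniform within strata, with the upper stratum spanning 13 years (6 to just under 19). The share without Tanner staging is s + (1 − s) × k/13. Here k = 1 if staging starts at exact age 7, and k = 2 if it starts at 8 completed years.

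- s = 0.4, k = 1: 0.4 + 0.6 × 1/13 = 0.45
- s = 0.6, k = 2: 0.6 + 0.4 × 2/13 = 0.66

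So about 45% to 66% on these assumptions.

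**3. Sensitivity of a pooled mean level to a few children**

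All levels here are assumed. The prepubertal mean is 1 (SD 0.3), and the pubertal mean is R (SD 0.6R). Two prepubertal children rise from 1 to 5, which adds 2 × 4 = 8 to the arm total.

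For n = 45 with 14 pubertal children and R = 10:

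- Pooled mean: (14 × 10 + 31)/45 = 3.8
- Variance: [14 × (6.2² + 6²) + 31 × (2.8² + 0.3²)]/45 = 28.6
- Standard error: √(28.6/45) = 0.80
- Shift: 8/45 = 0.18, or 0.22 standard errors

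With 40 to 45 per arm, 20% to 40% pubertal and R from 5 to 20, the shift is about 0.1 to 0.6 standard errors. Among the 31 prepubertal children alone it is 8/31 = 0.26, against a standard error of 0.3/√31 = 0.054. This concerns levels at a visit, not change from baseline.

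**4. Medians and change from baseline**

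Take 45 children with fixed levels: 40 at 1 and 5 at 30.

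- *Two rise to 5.* The mean goes from 190/45 = 4.22 to 198/45 = 4.40. The median (23rd value), both quartiles and the maximum stay at 1, 1, 1 and 30. For change from baseline, the median and quartiles are 0, the mean is 0.18 and the maximum is 4.
- *Twenty double.* The values are 20 at 1, 20 at 2 and 5 at 30, so the median moves from 1 to 2. Mean change is 20/45 = 0.44. The SD of change is √[(20 − 45 × 0.444²)/44] = 0.50, so the shift is about 0.9 SD of change.

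The pooled table is therefore weak for a few children, but not for a shift across many.

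**The case against.** A reader might infer that precocious puberty in young children cannot be seen at all. The documents do not support that. SAP 6.4.9 lists every value with its reference range and low/high flag, and lists values outside sponsor alert ranges. The investigator reviews each laboratory report (Protocol 7.2.5). Clinically significant values become adverse events (Protocol 8.1.1), which are tabulated by arm (SAP 6.4.1.2). This stands: individual cases can be found. It has limits. The alert ranges are not given, the SAP does not say that reference ranges depend on age and sex, and the adverse event route turns on each investigator's judgement. Listings show cases but do not compare arms.

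A reader might also infer that adolescents dominate the means. With pubertal fraction p and level ratio R, their share of the pooled total is pR/(pR + 1 − p). That is 25% at p = 10% and R = 3, and 97% at p = 40% and R = 50. The documents give neither quantity, so dominance is possible but not shown.

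Nor is any effect necessarily swamped. SAP 6.1.1 reports medians, quartiles and ranges, and step 4 shows a broad shift doubling the pooled median. Dividing that 0.44 shift by the between-child SD of levels in the same example (9.2) gives 0.05. That sets a change against the wrong SD. Change from baseline removes fixed differences between children and adolescents, so chance imbalance in adolescents matters mainly for raw levels.

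Finally, precocious puberty is neither a named safety objective nor an adverse event of special interest, and these tables are descriptive. That limits the priority but does not remove the gap.

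**Conclusion.** The point holds in a limited form. The pooling over sex and the lack of any committed age split follow from the text alone. So does the absence of Tanner staging at 7 or under, and of a by-arm count of high hormone values. For a few young children, detection rests on flagged listings and adverse event reports, and no planned by-arm summary of the hormone values is suited to the purpose.

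The size, about 0.1 to 0.6 standard errors of a pooled arm mean for two children rising fivefold, rests on assumed hormone levels, spreads and age mix. It applies to levels, not to change. It illustrates insensitivity and is not an estimate for this trial. The point has no bearing on efficacy or on the type I error rate. It is a worthwhile, inexpensive improvement to a safety table.

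**What to change.** In SAP 6.4.9 and Table 14.3.4.5b, present LH, FSH, estradiol, testosterone and IGF-1 by arm within sex and a coarse age split: 7 years or under, and over 7. Add n (%) per arm, in the same cells, with a post-baseline value newly above the laboratory's age- and sex-specific upper limit. Confirm first that the central laboratory's limits are of that kind, because the count means little otherwise. Add a hormone extreme-value listing to Appendix 1 so that it matches SAP 6.4.9.

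No new samples are needed. The cost is extra rows and small cells. Two sexes by two age groups give four cells per arm, averaging 45/4 = 11 children at the protocol's sample size or 40/4 = 10 at the SAP's. Splitting at 7 and again by the three Tanner bands would give 16 cells over both arms, or only 5 to 6 children each (80/16 to 90/16), so the coarse split is preferable. Cells may shrink further, because Protocol Table 13 ranks LH, FSH, estradiol and testosterone as Priority 3 and IGF-1 as Priority 4 when blood volume is restricted. The output should be labelled descriptive, with no tests.

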6.4.10 Columbia-Suicide Severity Rating Scale

Columbia-Suicide Severity Rating Scale data will be collected as per at screening visit (Visit 1), at randomization (visit 3), Titration period (at visit 6), maintenance period (at Visit 8 and 10) and at End of study visit (Visit 12).

Subjects who are younger than 7 years chronologically, or who are judged by the investigator not to have the mental capacity to understand the questions as specified on the C-SSRS, will not complete the rating. The investigator should use his/her judgment to substitute intellectually-appropriate questions to probe the tendency for self-harm.

If a subject with the intellectual capacity to complete the C-SSRS has their 7th birthday during the study, use of the C-SSRS should be initiated at subsequent visits.

All individual subject C-SSRS data will be listed.

Suicidal Ideation:

The following outcomes are C-SSRS categories for suicidal ideation and have binary responses (yes/no):

Category	Outcome Description
1	Wish to be dead
2	Non-specific active suicidal thoughts
3	Active suicidal ideation with any methods (not plan) without intent to act
4	Active suicidal ideation with some intent to act, without specific plan
5	Active suicidal ideation with specific plan and intent

Suicidal Behavior:

The following outcomes are C-SSRS categories for suicidal behavior and have binary responses (yes/no):

Category	Outcome Description
6	Preparatory acts or behavior

7	Aborted attempt
8	Interrupted attempt
9	Actual attempt (non-fatal)
10	Completed suicide

Suicidal behavior is assessed as a “yes” answer at any time during the T + M period to any one of the five questions (6-10) above. The number and percentage of subjects who had suicidal behavior, as well as the number and percentage having a “yes” response to each category (6-10) at least once during the T + M period. The denominator will be the number of subjects completing the C-SSRS at least once during the T + M period.

Self-injurious behavior without suicidal intent:

The number and percentage of subjects having reported anytime during the T+M period experiencing a ‘Self-injurious behavior without suicidal intent’ event (Question 11) will be provided.

6.4.11 Brief Rating Inventory of Executive Function (BRIEF)

The Behavior Rating Inventory of Executive Function (BRIEF™) and its preschool version, BRIEF-P, are standardized, validated rating scales to measure executive function in children within the home and school environments that will be assessed by the parent according to the schedule in [Table 1](#) (i.e. at Randomization (Visit 3), at Maintenance period (Visit 8) and at End of study visit (Visit 12)).

The BRIEF measures multiple aspects of executive functioning; scales include Inhibit, Shift, Emotional Control, Initiate, Working Memory, Plan/Organize, Organization of Materials and Monitor.

The original BRIEF was the basis for the development of the BRIEF-P. The BRIEF-P Rating Form consists of 63 items that measure various aspects of executive functioning: Inhibit, Shift, Emotional Control, Working Memory, and Plan/Organize.

For the BRIEF and the BRIEF-P, mean scores at Baseline, End of Study/ET and mean change from baseline to End of Study/ET, and descriptive statistics will be presented by treatment group for the Safety population (SAF). The change from baseline in the ZX008 and placebo groups will be compared using Wilcoxon tests.

